This is a multicenter, randomized, clinical trial that will involve a minimum of 480 opiate abusers seeking opiate maintenance treatment. The study will be conducted at 10-12 sites with a maximum of 60 patients enrolled per site. Patients will be recruited at a rate of about 2 per week at each study site. Patient recruitment will last 30 weeks. Patients will remain on study medication for 16 weeks. After eligibility screening and signing a written informed consent, patients will be randomly assigned to one of four treatment groups: buprenorphine 1, 4, 8, or 16 mg/day. About 120 patients will be assigned to each group. Each site will enroll 15 patients into each group.

Patients will be administered their buprenorphine dose daily. No takeout dosages of medication will be allowed. Study sites will dispense buprenorphine 7 days per week.

After patients complete the 16-week protocol, they may be continued on the study drug under a new protocol or offered other treatment available at clinic. Patients who wish to be tapered from buprenorphine will be administered the induction schedule in reverse. If resources are available at the site, eligible patients can be switched to methadone or other treatments available after they are tapered from the buprenorphine. Otherwise, they will be tapered off the drug.

Inclusion Criteria

- 1. DSM-III-R diagnosis of current *opiate dependence* with daily use for past month.
- 2. Male and non-pregnant, non-nursing female, ages 18 or older.
- 3. Mentally competent to give informed consent.
- 4. Agreeable to being in protocol (signs informed consent).
- 5. Permanent residence within commuting distance of clinic.
- 6. Urine negative for methadone.

Exclusion Criteria

- 1. Acute hepatitis or any other acute medical condition that would make participation in the study medically hazardous for the patient, e.g., active tuberculosis, unstable cardiovascular or liver disease, unstable diabetes, or AIDS (not HIV-positive alone). Patients with elevated liver enzymes (SGOT or SGPT greater than 5 times the upper limit of normal) require more frequent clinical and laboratory monitoring than those specified in the schedule of data collection. Those with liver enzymes exceeding 8 times the upper limit of normal require at least weekly clinical and laboratory examinations and consultation from a specialist in liver disease before enrollment.
- 2. DSM-III-R diagnosis of current alcohol dependence or sedative-hypnotics dependence.

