In order to provide a comparison group for safety measures included in this study, "scooped" data from methadone patients treated at the individual sites will be gathered during the course of this extension protocol. This information will reflect the number of patients followed at the clinic, the demographic descriptors of those patients, the dose of methadone received, numbers of program drop outs/terminations, and adverse events. It is anticipated that adverse event reporting for the methadone patients may not be as extensive as it is for the study patients. To the extent methadone adverse experience data are available for reporting, they will be used for comparison to the experience of patients participating in this extension amendment. No patient identifiers will be reported with these data; only the aggregate data normally reported to governmental agencies will be utilized for this comparison.

There are several compelling reasons to collect longer term safety data on buprenorphine in opiate addicts:

- 1. the safety data derived from buprenorphine analgesia patients may not be applicable to this population because opiate addicts may require higher buprenorphine doses than used for analgesia and longer duration of dosing compared to analgesia patients;
- 2. opiate abusers often take a variety of other street drugs and prescription medications, increasing chances of unanticipated drug-drug interactions compared to pain patients; and
- 3. many opiate abusers have pre-existing liver disease or other chronic illnesses. Hence prior safety data of buprenorphine in pain patients is not entirely relevant for opiate addicts.

In addition to long term safety data, this protocol amendment permits the gathering of limited self report and observer reported data with regard to the dose modification including the newly added 32 mg dose. This information is not intended as efficacy data, but will be reported in labeling language descriptively characterizing the dosing experience among these patients during the extension amendment.

It is also expected that amending this protocol to provide for extended dosing will enhance retention in the original protocol. It could be expected that compliance will increase because:

- 1. subjects will be less likely to terminate if a regular methadone treatment slot were to become available to them

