4.0 STUDY DESIGN

This extension amendment provides drug dosing to all patients who successfully complete the original protocol 999a and any applicable continuation of that parent protocol for an aggregate total of 52 weeks. Compared to the parent protocol and applicable continuations, this amendment permits:

- the study sites to collect and analyze urine specimens for drug screening purposes. These results will be used by the investigators for dose modification and counseling purposes.
- 2. dose modification to the next higher or lower dose. This modification may be made at any time during the course of this amendment. An additional dose of 32 mg will be added to the dosage range to permit escalation from the current highest study dose (16 mg) in the parent protocol. There are no limits to the number of dose modifications that can be made during the extension (no more than one dose change per day). At the time of enrollment or any time thereafter patients in the extension protocol and their treating physician may choose to double or to halve the individual's dose. These modifications may occur as

frequently as deemed clinically indicated, but in no instance will the dose increase beyond 32 mg/day or decrease to less than 1 mg/day.

- 3. reduction of clinic attendance to 5 or 6 days per week depending upon the decision of study site personnel. Because take home doses will not be permitted, a double dose not to exceed 32 mg will be administered on clinic day 5 or 6.
- 4. reduction of frequency and extensiveness of assessment.

Previous studies indicate that doses up to 32 mg/day have been safely tolerated even in normal volunteers (Walsh, et al, 1992a). Prior work has also indicated that withdrawal symptoms from fixed doses of 8 mg. of buprenorphine appear after 48-72 hours (Fudala, et al, 1990). Hence doubling doses is expected to provide coverage from withdrawal symptoms during the weekend dosing schedule.

All patients who enroll in this extension will be maintained on buprenorphine in a double blind status until the last eligible patient at all sites has completed 12 additional weeks of dosing after the parent protocol or has been terminated. At that time the study can be opened for an investigator to know the dose of buprenorphine being administered to any given patient.

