7.0 STUDY EXECUTION

7.1 Treatment

Number of subjects:

All subjects at each of 12 centers who have been receiving buprenorphine continuously and successfully completed parent protocol (#999a) and any applicable continuation.

Subject replacement/addition:

None

Premature Withdrawals:

If a subject either leaves the study voluntarily prior to completion or is terminated by the staff, the circumstances, if known, will be documented in the subject's study record and recorded on Form 08. In addition, PCC will be notified by each site when a subject is terminated.

Method of drug administration:

Medications will be administered by dispensing personnel, exactly as in the parent protocol. All staff at participating sites will remain blind to the subjects' doses except as discussed previously. As in the parent protocol, subjects will hold the medication under their tongue for 5 minutes following the sublingual dosage to assure maximal absorption.

Dose Schedule:

The number of dosing adjustments will be at the investigators' discretion, but each time a dosing change is made, the reason must be fully documented in the case report form. The doses available are: 1, 2, 4, 8, 16, and 32 mg. (A 12 mg dose also is available, but this dose only occurs in the reinduction and taper paradigms and is not a maintenance dose.) The highest maintenance dose available is 32 mg and the lowest is 1 mg.

As in the parent protocol, no take home doses will be allowed. Subjects must attend the clinic either Monday through Friday or Monday through Saturday, depending upon at which site the subject is enrolled.

The following sites will operate on a Monday through Friday schedule:

Hines VA
Boston VAOPC
New York VA

San Juan VA
San Francisco General
San Francisco VA

Those operating on a Monday through Saturday schedule are:

Milwaukee County Medical Complex West Haven VA Philadelphia VA

Subjects will receive a double dose of their study medication on either Fridays or Saturdays to eliminate the need for a Saturday and Sunday or a Sunday clinic visit, respectively. This is expected to "hold" the subject until Monday, but the results of this study will be more definitive in this regard.

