8.0 CRITERIA FOR RESPONSE

Measures and Measuring Instruments:

Those variables used primarily to evaluate safety are:

- 1. Adverse experiences will be evaluated at the time of entry into the extension protocol and weekly thereafter as in the parent protocol.
- 2. Laboratory data CBC, UA, SMA-12 will be collected every twelve weeks and EKGs will be taken 24 weeks after the completion of the parent protocol and at the termination.

Those variables which will be used primarily to provide descriptive analyses of method modifications (dose adjustments, dosing schedule, doubled weekend doses) for inclusion in "directions for use" label language are:

- 1. Self reported frequency of illicit drug and ethanol use will be obtained every week.
- 2. Abbreviated self report including reports of opiate side effects and withdrawal symptoms.

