9.0 STATISTICS

This extension is intended primarily to gather longer term safety data. Safety parameters to be analyzed both descriptively and as group and paired t-tests utilizing all data generated on participating patients are:

- 1. All safety parameters (adverse events, protocol discontinuation, laboratory studies)
- 2. Dose adjustment, dose schedule modification, and doubled weekend doses compared to parent protocol data for safety variables (#1 above)

Analysis of safety data will include both relevant data from the extension amendment period as well as the prior parent protocol and applicable continuation amendments. Thus, the period of analysis for all subjects will be for up to one year, or until the point of termination from the study.

Modifications of methods in this extension amendment will also permit consideration of data relevant to these modifications. These modifications are:

- 1. unblinding of the results of urine toxicology tests, allowing each site to perform its own drug screening to monitor illicit drug use
- 2. adjustment of dosage including a new 32 mg dose
- 3. reduction of clinic attendance to 5 or 6 days per week depending upon the decision of study site personnel
- 4. doubling of weekend dosage in place of take home dosages.

A descriptive analysis of these modifications relevant to safety and outcome will be completed, dependent in part of the number of patients who opt to modify their dose. This extension amendment provides data for the following analyses:

- 1. Percent patients experiencing opiate withdrawal including craving or side effects by dose and dosing pattern (5 or 6 day dosing)
- 2. Percent missed doses by day of the week and by dose level of buprenorphine.

All comparisons with the parent protocol will be made by displaying the measures graphically and by using simple t-tests. The comparisons with the parent protocol will be made using the data for all patients from the parent protocol as well as for only those patients who were allowed to enter the extension protocol. The latter comparison will enable us to evaluate the usefulness of the extension protocol for those patients who crossed over to the extension protocol.

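### The extension's withdrawal analysis is untimed and its 5- v 6-day split is fixed by site, so it cannot by itself show whether the doubled weekend dose holds until Monday; one calendar-day table from data already collected would help.

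*Combined protocol and SAP*

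**What the plan says.** Section 7.1 of the extension (Dose Schedule) has patients attend five or six days a week according to their site. A double dose on the last clinic day covers the gap: "This is expected to 'hold' the subject until Monday, but the results of this study will be more definitive in this regard". Section 4.0 gives the reasoning: "withdrawal symptoms from fixed doses of 8 mg. of buprenorphine appear after 48-72 hours", so doubling is expected to cover the weekend. Section 8.0 lists doubled weekend doses among the method changes to be described for directions-for-use label language. The variables it assigns to that purpose are weekly self-reported drug use and "Abbreviated self report including reports of opiate side effects and withdrawal symptoms".

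Section 9.0 then names two analyses:
- Analysis 1: "Percent patients experiencing opiate withdrawal including craving or side effects by dose and dosing pattern (5 or 6 day dosing".
- Analysis 2: "Percent missed doses by day of the week and by dose level of buprenorphine".

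Section 9.0 also lists, among the safety parameters, "doubled weekend doses compared to parent protocol data for safety variables (#1 above". Comparisons with the parent protocol are to use all parent patients and, separately, only those who entered the extension. In the parent protocol (Method), "Study sites will dispense buprenorphine 7 days per week".

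**The concern.** Whether a dose holds until Monday is a question about when symptoms occur relative to the last dose. Analysis 1 counts patients. A symptom on a Wednesday, the day after a dose, counts the same as one on a Sunday night. Its only link to gap length is the 5- or 6-day pattern, and that is a property of the clinic. A difference between patterns may reflect the gap, or differences between clinics in patients, staff and recording.

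Day of the week appears in section 9.0 only for missed doses. At stake is the quality of the description of weekend dosing that section 8.0 intends for label language: as listed, the withdrawal figures do not separate days without a dose from days with one.

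**Working it through.** The plan gives no rate, power or sample size for this analysis, so there is no figure to reproduce. The check has five steps.

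**1. Does a percent of patients carry timing?** Let W be the percent affected in a week (assumed values).
- Even daily risk d: W = 1 − (1 − d)^7.
- Risk w on Sunday and Monday only: W = 1 − (1 − w)^2.

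| W | d (every day) | w (Sunday and Monday only) |
|---|---|---|
| 10% | 1.5% | 5.1% |
| 30% | 5.0% | 16.3% |
| 50% | 9.4% | 29.3% |

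Both columns give the same W, so analysis 1 cannot tell them apart. A dated table could: evenly spread onsets would put 2/7 = 28.6% on Sunday and Monday.

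**2. Can pattern be separated from site?** Section 7.1 lists six Monday–Friday sites and three Monday–Saturday sites. A design matrix of 9 site indicators has rank 9. Adding the pattern gives 10 columns and still rank 9, so pattern is wholly aliased with site. Nine of the 12 centers appear in that list; this does not alter the aliasing.

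**3. Which days matter?** Friday to Monday is 3 × 24 = 72 h, and Saturday to Monday is 2 × 24 = 48 h. The 48–72 h window in section 4.0 therefore runs from Sunday to the Monday dose at 5-day sites, and is only reached at about the Monday dose at 6-day sites. That window is stated for fixed 8 mg doses; applying it to a doubled dose is an assumption.

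**4. Why does Monday need its own row?** Dates carry no clock time, so onsets before the Monday dose cannot be separated from later ones. Suppose Monday carries the same rate ratio RR as the no-dose days but is pooled with dosed days. The apparent ratio is then:
- 5-day sites: RR / ((RR + 4)/5), which is 1.67 for RR = 2 and 2.14 for RR = 3.
- 6-day sites: RR / ((RR + 5)/6), which is 1.71 and 2.25.

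**5. Can the 5- v 6-day difference be sized?** Not from the documents. Purely as illustration, assume p onsets per dosed day, a ratio RR on the days of excess, and percent ever affected = 1 − exp(−expected onsets).
- Excess on all no-dose days, RR = 2, over 36 weeks: expected onsets 36(5 + 2RR)p v 36(6 + RR)p. For p = 0.001, 0.005 and 0.01 this gives 27.7 v 25.0%, 80.2 v 76.3% and 96.1 v 94.4%, or 2.7, 3.9 and 1.7 points.
- The same at p = 0.01, read per week: 1 − exp(−0.09) v 1 − exp(−0.08) = 8.6 v 7.7%, or 0.9 points.
- Excess on Sunday and Monday at 5-day sites only, RR = 3, p = 0.005, over 36 weeks: 1 − exp(−1.98) v 1 − exp(−1.26) = 86.2 v 71.6%, or 14.6 points.

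The result depends on the assumed rate, the window and the Monday risk. None is in the documents.

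**Data available.** Form 06 has a code for withdrawal symptoms (code 4) with onset and resolution dates. Form 09 is kept daily, with date, weekday and weekend dose, missed dose and day off. Over at most 36 weeks, a 5-day patient contributes up to 72 no-dose days, 36 Mondays and 144 other dosed days; a 6-day patient up to 36, 36 and 180. Time in a continuation reduces these, because the 52-week limit includes it.

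**The case against.** The strongest reply is that the plan does not rest on analysis 1. Section 4.0 plans safety variables by dose, dose modification and other drug use, and section 9.0 counts adverse events and discontinuation as safety parameters. Section 8.0 assigns weekly self-reported drug use to describing doubled weekend doses, and Form 04 already splits that use into Friday–Sunday and Monday–Thursday. Section 9.0 promises a descriptive analysis of all four modifications. The parent comparison in extension entrants avoids the site confounding. This stands, and a reader who inferred that the plan has nothing else on weekend dosing would be wrong. But none of these items times withdrawal. The parent comparison also coincides with flexible dosing, site access to urine results and later time in study. Continuation dosing under parent procedures at some sites offsets the last of these in part.

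A reader might also infer that the sponsor plans a label claim that the doubled dose holds. The documents do not say so. The Synopsis sentence "This information is not intended as efficacy data, but will be reported in labeling language descriptively characterizing the dosing experience among these patients" concerns dose modification, including the new 32 mg dose, and does not mention weekend doses. Section 8.0 does, but only as description, in an extension intended primarily for longer-term safety.

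Finally, a within-patient table alone would not settle the question, because the dosing gap falls on the calendar weekend every week. That is correct, and it is why the fix includes the same tabulation under 7-day dosing.

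**Conclusion.** The concern holds in a limited form. Analysis 1 has no timing term and its pattern is aliased with site, so by itself it cannot show whether the doubled dose holds until Monday. The other planned items bear on the question without timing withdrawal.

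No size in percentage points should be attached: the illustrations run from 0.9 to 14.6 points on assumed inputs alone. Nor do the documents support reading the gap as a threat to any test, sample size or safety conclusion. This is a cheap improvement to a descriptive analysis whose data are already collected. The conclusion rests on section 9.0 as written, on the site list in section 7.1, and on Forms 06 and 09 being completed as designed.

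**What to change.** Add one descriptive table to section 9.0: Form 06 withdrawal symptoms by calendar day relative to the last administered dose on Form 09.

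- Rows: no-dose days (Saturday and Sunday separately at 5-day sites, Sunday at 6-day sites); Monday; other dosed days.
- Show onsets, and beside them days with a symptom present from onset to resolution.
- Present by current dose, with 32 mg apart because section 7.1 does not double it.
- Leave out days after a missed dose and reinduction or taper days.
- Where parent or continuation adverse-event dates allow, give the same day-of-week tabulation for the same patients under 7-day dosing, so that the dosing gap can be told apart from an ordinary weekend effect.
- Report as supportive the weekly Form 06 answer on whether the dose is holding, Form 08 terminations because the drug was not holding, and the Form 04 split.
- Keep the planned parent comparison, and label the 5- v 6-day percentages as a between-site description.

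The cost is programming for one table and a few supportive lines, with no new data collection. State its limits: onset dates are recalled over a week and carry no clock time, a recurring symptom may be entered once, and weekends differ socially from weekdays. The table describes; it does not prove that a dose held or failed.

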Patient taking buprenorphine (sublingual) 1mg, 2mg, 4mg, 8mg, 12mg, 16mg, or 32mg.

[Adhesive-backed label]

(COLOR: FLUORESCENT GREEN)

CASE REPORT FORM BOOK LABELS

Participant In VA/NIDA Study #999a Extension

Buprenorphine VA/NIDA Study #999a Extension "A Multicenter Clinical Trial of Buprenorphine In Treatment of Opiate Dependence"

Patient Initials:	Patient Initials:	
Randomization #:	Randomization #:	

(COLOR: WHITE BACKROUND WITH GREEN PRINT)

PRESCRIPTION RUBBER STAMPS

VA/NIDA STUDY #999a Extension DRUG CODE NAME: B-999AE (Buprenorphine 1, 2, 4, 8, 16, or 32mg) Patient Randomization #: WEEKDAY DOSE: [Monday through Thursday or Friday] Drawer #: Units Dispensed: ONE dose daily during the week. Directions: Place contents of one container under the tongue daily.
VA/NIDA STUDY #999a Extension DRUG CODE NAME: B-999AE (Buprenorphine 1, 2, 4, 8, 16, or 32mg) Patient Randomization #: WEEKEND DOSE: [Friday or Saturday] Drawer #: Units Dispensed: ONE dose every weekend. Directions: Place contents of one container under the tongue daily.
VA/NIDA STUDY #999a Extension DRUG CODE NAME: B-999AE (Buprenorphine 1, 2, 4, 8, 12, 16, or 32mg) Patlent Randomization #: Drawer #: Circle Regimen: Reinduction, OR Taper Circle Dose Dispensed: Dose #1; Dose #2; Dose #3; Dose #4 Directions: Place contents of one container under the tongue daily

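### Extension section 9.0, analysis 2: missed doses by weekday are not split by dosing pattern, so the Friday figure mixes a doubled weekend dose with an ordinary dose

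*Combined protocol and SAP*

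**What the plan says.** Section 9.0 of the extension lists two descriptive analyses of the changed methods. The first is "Percent patients experiencing opiate withdrawal including craving or side effects by dose and dosing pattern (5 or 6 day dosing"). The second is "Percent missed doses by day of the week and by dose level of buprenorphine". The second gives no split by dosing pattern and defines neither numerator nor denominator.

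Section 7.1 (Dose Schedule) sets the day of the doubled dose: "Subjects will receive a double dose of their study medication on either Fridays or Saturdays", depending on the site. Six sites follow "The following sites will operate on a Monday through Friday schedule" and three follow "Those operating on a Monday through Saturday schedule are". The prescription stamp in Appendix A labels the ordinary dose "WEEKDAY DOSE: [Monday through Thursday or Friday", so at a Monday-Saturday site Friday is a weekday dose and Saturday is the weekend dose. Section 7.1 also says that the doubled dose is given as a single vial, and that patients maintained on 32 mg are not doubled on the weekend-dose day.

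On comparison with the earlier phase, section 9.0 says "All comparisons with the parent protocol will be made by displaying the measures graphically and by using simple t-tests". In the parent protocol (Method), sites dispensed seven days a week.

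**The concern.** A day-of-week table is informative only if a given weekday means the same thing for everyone in the cell. Here Friday does not. At a 5-day site it is the one visit meant to carry the patient to Monday. At a 6-day site it is one of five ordinary weekday doses. The plan recognises the two patterns in analysis 1 and leaves them out of analysis 2.

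What is at stake is whether the table can answer its own question. Objective 5 in section 3.0 is to describe experience with the modified methods for directions-for-use language, and the doubled weekend dose is one of those modifications. How often that dose is missed is a natural thing to want from this analysis. For the 5-day sites it cannot be read from the table as specified.

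The open denominator adds a second problem. If the weekday figures are added to a weekly total and set against the parent protocol, the total runs over 5 or 6 scheduled doses in one phase and 7 in the other.

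**Working it through.** The plan states no figure for this analysis, so there is none to reproduce.

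**Inputs.** From section 7.1: six 5-day sites and three 6-day sites. The same section refers to 12 centers, so the lists cover nine of them. From the parent protocol: 7 dosing days a week. The documents give no missed-dose rates and no numbers of patients per site in the extension. The rates below and equal site sizes are therefore assumptions.

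**1. The pooled Friday.** Let p5 be the Friday miss rate at 5-day sites (doubled dose) and p6 the rate at 6-day sites (ordinary dose).

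Pooled = (6·p5 + 3·p6)/9, so pooled − p5 = (p6 − p5)/3.

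| p5 | p6 | Pooled Friday | Error for the doubled dose |
|---|---|---|---|
| 30% | 10% | (1.8 + 0.3)/9 = 23.3% | −6.7 points |
| 20% | 20% | 20.0% | 0 |
| 10% | 30% | (0.6 + 0.9)/9 = 16.7% | +6.7 points |

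The error has the sign of p6 − p5, which the documents do not give.

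**2. One vial or two doses?** Within one weekday at one type of site, the counting rule makes no difference: 12 missed of 60 is 20%, and 24 of 120 is 20%. It matters only when days or site types are combined.

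**3. Whole-week totals at a 5-day site.** Let p be the Monday-Thursday rate and pF the Friday rate.

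- Per scheduled dose: (4p + pF)/5.
- Counting a missed Friday dose as three calendar days: (4p + 3pF)/7.

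With p assumed at 20%:

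| pF | Per scheduled dose | Calendar-day count |
|---|---|---|
| 10% | 18.0% | 15.7% |
| 20% | 20.0% | 20.0% |
| 30% | 22.0% | 24.3% |
| 40% | 24.0% | 28.6% |

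At a 6-day site, with pS the Saturday rate, the formulas are (5p + pS)/6 and (5p + 2pS)/7. They give 18.3% and 17.1% at pS = 10%, and 23.3% and 25.7% at pS = 40%. The scheduled-dose total is lower than the calendar-day count only when the weekend dose is missed more often than the others. It is higher when that dose is missed less often.

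**4. The same absence in the two phases (5-day site).**

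- Friday to Monday: parent 4/7 = 57%, extension 2/5 = 40%.
- Monday to Wednesday: parent 3/7 = 43%, extension 3/5 = 60%.
- Averaged over all seven start days, an absence of L days removes 5L/7 scheduled doses. As a share of 5 this is L/7, the same as in the parent.

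**The case against.** The strongest reply is that this is a descriptive table with no hypothesis or decision rule, and that an analyst can recover the split. Form 09 has one row per calendar day, with *Missed Dose* separate from *Day Off*, and each listed site's schedule is fixed. Section 8.0 does not list missed doses among the variables used primarily for directions for use. For parent comparisons, section 9.0 names the safety variables explicitly and does not name missed doses. All of this stands, and it keeps the point minor. It does not rescue the analysis as written, which asks for a weekday table without the split even though the data would allow it.

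A reader might go further and infer that the new schedule is made to look better attended than it is. The argument would be that a patient who never comes for the weekend dose scores 1/5 = 20% or 1/6 = 17%, while the same days in the parent score 3/7 = 43% or 2/7 = 29%. The documents do not support this, for three reasons:

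- The doubled dose is one vial at one visit, so missing it is one missed visit. Attendance is not miscounted. What differs is the time without drug.
- Those fractions are whole-week totals for an extreme patient, and the plan does not specify whole-week totals. In the planned table that patient is 100% missed on the weekend-dose day.
- The bias is zero under equal miss rates and reverses for a Monday-Wednesday absence.

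Nor is it right that the table says nothing about weekend doses. Saturday maintenance doses come only from 6-day sites and are their weekend dose. Even there the denominator needs stating, because Appendix A wants reinduction doses available on Saturdays and Sundays.

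**Conclusion.** The point holds as a limited one. Analysis 2 omits the dosing-pattern split that analysis 1 has, so its Friday cell combines two different doses. On the nine listed sites with equal numbers, the cell misstates the doubled-dose miss rate by one third of the difference between the two Friday rates, for instance 6.7 points when they differ by 20. The direction is unknown, and the one-third weight would change with the real site sizes and with the schedules of any further centers.

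The difference in denominators matters only if missed doses are totalled over the week and compared with the parent protocol, which section 9.0 neither clearly includes nor excludes. That bias also has no fixed sign. Nothing in the documents shows that the analysis favours the extension. No confirmatory conclusion depends on this table.

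**What to change.** Reword analysis 2 in section 9.0 as follows:

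- Report percent missed by dose type (weekday or weekend dose) and maintenance dose level, separately for 5-day and 6-day sites. A day-of-week display may be kept within each pattern.
- Define the denominator as scheduled doses, excluding days recorded as *Day Off*, and say how reinduction doses are handled.
- Show the 32 mg level apart in any weekend-dose summary, because its weekend dose is not doubled.
- If missed doses are compared with the parent protocol, use only days that carry an ordinary single dose in both phases: Monday-Thursday at 5-day sites and Monday-Friday at 6-day sites.
- Calendar days without drug may be added as a separate descriptive measure. It should not presume that the doubled dose covers the weekend. Section 7.1 treats that as an expectation on which the study is to be more definitive.

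The cost is a few lines of wording. Form 09 already holds the data. Its weekday-dose and weekend-dose boxes sit under doses administered, so the type of a missed dose should be assigned from the day of the week and the site's schedule.
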